
Title of Study: A Randomized, Double-Blind, Placebo-Controlled, Phase 2 Study to Assess the Efficacy, Safety, and Tolerability of Cannabidiol Oral Solution for the Treatment of Patients with Prader-Willi Syndrome

Study Center(s): Approximately 10 sites in the US and Canada

Study Period: Estimated date first patient enrolled: Mar 2018 Estimated date last patient completed: Mar 2019

Phase of Development: Phase 2

Objectives:
 
Primary:
 
 • To assess the efficacy of Cannabidiol Oral Solution on hyperphagia-related behavior in patients with Prader-Willi Syndrome (PWS) as measured by total score of the Hyperphagia Questionnaire for Clinical Trials (HQ-CT). 
Secondary:
 
 • To assess the efficacy of Cannabidiol Oral Solution on the change in total body-weight in patients with PWS. • To assess the responder rate (responder is defined as 6-point decrease on the HQ-CT from Baseline to End of Study). • To assess the efficacy of Cannabidiol Oral Solution by measuring the changes in Patient Global Impression of Change (PGI-C). • To assess the safety and tolerability of Cannabidiol Oral Solution in patients with PWS. • To assess the efficacy of Cannabidiol Oral Solution on eating behavior in patients with PWS as measured by the Three Factor Eating Questionnaire-18-item version (TFEQ-R18). • To assess the impact on Quality of Life in patients with PWS as measured by the PROMIS® Life Satisfaction and Positive Affect short-form questionnaires.

- To assess the impact on physical activity in patients with PWS as measured by the PROMIS Physical Activity and Fatigue questionnaires.

Exploratory:

- To assess the efficacy of Cannabidiol Oral Solution on body composition, and bone mineral density, as measured by dual-energy X-ray absorptiometry (DEXA).

Methodology:

This is a double-blind, randomized, placebo-controlled, Phase 2 clinical trial in patients diagnosed with Prader-Willi Syndrome. Patients will receive either Cannabidiol Oral Solution (40 mg/kg/day) or placebo with patients randomized in a 1:1 ratio. Randomization will be stratified according to use of growth hormone treatment.

Approximately 66 male and female patients aged 8 to 17 years, inclusive, with a genetically confirmed diagnosis of Prader-Willi Syndrome will be enrolled in the study.

The study will consist of the following six periods:

- Screening Period (2 weeks)
- Placebo Lead-In Period (2 weeks)
- Titration Period (1 week)
- Maintenance Period (12 weeks)
- Taper Period (1 week)
- Follow-Up Period (1 week)

Patients who meet entry criteria will be assigned to a 2-week single-blind Placebo Lead-In Period. Following the placebo single-blind lead-in period, patients will be randomly assigned to receive double-blind treatment with either Cannabidiol Oral Solution treatment at a dose of 40 mg/kg/day or matching placebo divided twice daily with standard meal (a 1-week Titration Period followed by a 12-week Maintenance Period). During the Titration Period, Cannabidiol Oral Solution will be titrated as follows: Days 1-3: 20 mg/kg/day, Days 4-6: 30 mg/kg/day, Day 7: 40 mg/kg/day. The Investigator or designee will call on Day 3 and Day 6 to determine if the patient's dose may be titrated to the next dose level. If the Investigator determines that the patient is unable to tolerate the higher dose, the patient should be withdrawn from the study.

During the Maintenance Period, patients may have their dose of blinded study medication adjusted down to 30 mg/kg/day at the discretion of the Investigator or qualified designee based on the patient's tolerability.

After completion of the study, patients will be offered the opportunity to enroll in an open-label, long-term safety study. Patients who do not elect to enroll in the long-term safety study will be tapered off the study drug over 7 days according to the following schedule: 40 mg/kg/day to 30 mg/kg/day for 3 days, 30 mg/kg/day to 20 mg/kg/day for 3 days, discontinuing the drug on Day 7. A final safety follow-up will be conducted 2 weeks after study completion (Visit 10) for patients who do not elect to continue into the long-term safety study.

Safety assessments for all patients will include medical history, physical examination, vital signs (seated blood pressure, pulse rate, temperature, and respiration rate), clinical laboratory testing (including a CBC test), 12-lead ECG, urine drug screen (including THC), prior medication history, concomitant medication, and AE assessments.

Blood draws for PK sampling will be taken prior to medication dosing at specific study visits for determination of the plasma levels of CBD and 7-OH-CBD.

Number of patients (planned):

Approximately 66 male and female patients will be enrolled to have 60 patients (30 patients per treatment group) complete the study.

Diagnosis and main criteria for inclusion:

Patients will be male and non-pregnant female volunteers between 8 and 17 years of age (inclusive) with a genetically confirmed diagnosis of Prader-Willi Syndrome using a standard DNA methylation test or fluorescent *in situ* hybridization, able to understand and provide written consent, and who meet all the inclusion and none of the exclusion criteria.

Inclusion Criteria

1. Patient and/or parent(s)/caregiver(s) fully comprehend the informed consent form (ICF) and assent form, understand all study procedures, and can communicate satisfactorily with the investigator and study coordinator, in accordance with applicable laws, regulations, and local requirements.
2. Males and females from 8-17 years of age, inclusive.
3. Genetically confirmed diagnosis of Prader-Willi Syndrome using standard DNA methylation test or fluorescent *in situ* hybridization. Documentation of genetically confirmed diagnosis of Prader-Willi Syndrome is acceptable.
4. A score of ≥ 10 on the HQ-CT.
5. A caregiver is available to complete the HQ-CT.
6. If female, is either not of childbearing potential (defined as premenarchal or surgically sterile [bilateral tubal ligation, bilateral oophorectomy, or hysterectomy]) or practicing one of the following medically acceptable methods of birth control:
 - a. Hormonal methods such as oral, implantable, injectable, vaginal ring, or transdermal contraceptives for a minimum of 1 full cycle (based on the patient's usual menstrual cycle period) before study drug administration.
 - b. Total abstinence from sexual intercourse since the last menses before study drug administration.
 - c. Intrauterine device.
 - d. Double-barrier method (condoms, sponge, or diaphragm with spermicidal jellies or cream).
7. Adequate renal function, defined as serum creatinine $\leq 1.5 \times$ upper limit of normal (ULN) and urine protein/creatinine ratio <0.2 .

8. Adequate hepatic function, defined as total bilirubin $\leq 1.5 \times$ ULN and Aspartate aminotransferase (AST) and Alanine aminotransferase (ALT) levels $\leq 3 \times$ ULN.
9. Growth hormone treatment will be permitted if doses have been stable for at least 1 month prior to screening.
10. Psychotropic treatment will be permitted and should be stable at least 6 weeks prior to screening.
11. Any other treatment including thyroid hormones should be stable for at least 6 weeks prior to screening.

Exclusion Criteria

1. Known use of cannabis or cannabinoid-containing products for 4 weeks prior to baseline.
2. History of chronic liver disease, such as cirrhosis or chronic hepatitis due to any cause, or suspected alcohol abuse.
3. Use of weight loss agents or drugs known to affect appetite (including glucagon-like peptide-1[GLP-1] analogs) within 2 months prior to screening.
4. Uncontrolled Type I and Type II diabetes.
5. Currently taking concomitant medications that are strong cytochrome P450 3A4 (CYP3A4) or CYP2D6 inhibitors; or inducers of CYP3A4- or CYP2D6-sensitive substrates with a narrow therapeutic index.
6. Co-morbid condition or disease (such as respiratory disease, heart disease, or psychiatric disorder) diagnosed less than 1 month prior to screening.
7. History or presence of gastrointestinal or any other condition known to interfere with the absorption, distribution, metabolism or excretion of drugs as determined by the Investigator.
8. Patients who have participated in any other trials involving an investigational product or device within 30 days of screening or longer as required by local regulations.
9. Clinically significant abnormalities on ECG at screening or other evidence of heart disease as determined by the Investigator.
10. Has screening systolic blood pressure ≥ 160 mm Hg and diastolic blood pressure >100 mm Hg (may be repeated one additional time after 5 minutes' rest to verify). Patients with hypertensive levels lower than those specified may be excluded at the Investigator's discretion if deemed to be in the best interest of the patient.
11. Currently taking felbamate.
12. Uncontrolled sleep apnea.
13. Pregnant or lactating female.
14. History of hypersensitivity to drugs with a similar chemical structure or class as CBD.
15. Unwillingness or inability to follow the procedures outlined in the protocol.

16. Patient judged by the investigator or sponsor (or designee) as unable to comply with the treatment protocol, including appropriate supportive care, follow-up and research tests.
 
17. Positive drug screen, including THC, at time of screening.
 
18. Creatinine clearance test of < 30 mL/min.

Investigational product, dosage and mode of administration: Cannabidiol Oral Solution, 40 mg/kg/day, divided into twice daily doses with standard meal, manufactured for and supplied by Insys Development Company, Inc.

Duration of treatment: The maximum duration of the study from screening to follow-up will be approximately 19 weeks.


Reference therapy, dosages and modes of administration: Matching placebo, divided into twice daily doses with standard meal, manufactured for and supplied by Insys Development Company, Inc.

Criteria for evaluation:
 
Efficacy
 
Primary efficacy endpoint:
 
 • Change in the total score of the HQ-CT from Baseline (defined as the score after the 2-week Placebo Lead-In) through Study Completion (Week 13/Early Withdrawal). 
Secondary efficacy endpoints:
 
 • Change in total body-weight from Baseline through Study Completion/Early Withdrawal. • Responder rate (responder is defined as 6-point decrease on the HQ-CT) from Baseline through Study Completion). • Change in Patient Global Impression of Change (PGI-C). • Change in the TFEQ-R18 from Baseline through Study Completion/Early Withdrawal. • Change in the Quality of Life (PROMIS Life Satisfaction and Positive Affect short form pediatric questionnaires) from Baseline through Study Completion/Early Withdrawal. • Change in physical activity (PROMIS Physical Activity and Fatigue pediatric questionnaires) from Baseline through Study Completion/Early Withdrawal. 
Exploratory efficacy endpoint:
 
 • Change in body composition and bone mineral density from Baseline to Study Completion/Early Withdrawal as measured by DEXA. 
Safety

The safety endpoints are treatment-emergent AEs (TEAEs), clinical laboratory assessments, vital signs (blood pressure, pulse rate, respiration rate, and temperature), 12-lead ECGs, physical examination assessments, pregnancy screens, urine drug screen (including THC), medical history, and prior and concomitant medications.

Pharmacokinetic

- Trough concentrations (C_{trough}) of cannabidiol (CBD) and metabolite 7-hydroxy-CBD (7-OH CBD) will be used to assess the exposure-response relationship.

Statistical Methods:**Sample Size Calculation**

A total of 30 patients per treatment group will provide more than 85% power with an alpha of 0.05, for a difference in the HQ-CT from Baseline to Week 13 of 5 points with standard deviation of 6. Assuming a 20% drop out rate, approximately 66 patients (33 patients per arm) will be randomized to achieve 60 (30 patients/arm) completers.

Analysis Populations

Statistical analyses will be conducted on the following populations:

- Safety Population: The Safety Population will include all patients who were treated with at least one dose of the study drug.
- Intent to Treat (ITT) Population: The ITT Population will include all patients who were randomized.

Efficacy Analyses

The ITT Population will be used for all efficacy analyses.

The primary efficacy endpoint will be tested using a 2-sided type I error rate of 0.05. The primary outcome variable for the study is the change in total score of the HQ-CT from Baseline through Study Completion/Early Withdrawal.

Statistical inference for the primary endpoint and for the secondary endpoints (change in total body-weight, responder rate, PGI-C and PGI-S, TFEQ-R18, and PROMIS Life Satisfaction and Positive Affect, PROMIS Physical Activity and Fatigue), will be controlled at an overall family wise error rate (alpha) of 0.05, 2-sided.

For continuous endpoints, number of observations, mean, standard deviation (SD), median, minimum, and maximum, will be presented as descriptive statistics. For inferential statistics, analysis of covariance (ANCOVA) with the baseline value and randomization strata (growth hormone treatment) as covariates.

For categorical endpoints, the number of observations, frequency counts and percentages will be presented as descriptive statistics. Fisher's exact test will be used for inferential statistics.

Safety Analyses

The Safety Population will be used for all safety assessments.

All safety assessments will be descriptive and no inferential statistics are planned. All data listings will be provided for protocol specified safety data. The Medical Dictionary for Regulatory Activities (MedDRA; Version 20.0 or higher) will be used to classify all adverse events with respect to system organ class and preferred term. Adverse event summaries will include only TEAEs by treatment group. All clinical laboratory findings and vital signs will be summarized for all patients in the safety population for observed values and change from

baseline. Shifts from baseline according to normal range criteria will also be presented for all patients in the safety population. Prior medication and concomitant medications will be reported in the data listings.

Statistical analyses will be performed using SAS[®] (Version 9.3 or higher, SAS Institute Inc.).

Pharmacokinetic Analyses

Exploratory analyses of dose (exposure)-response relationship will be performed. Further population PK approach may be used for PK parameter calculations, as appropriate.

Missing Data

For efficacy measures, missing data points may be imputed using Jump to Reference as a conservative method. For safety data, there will be no imputation of missing data, and the safety assessments will be conducted based on the observed data.

Table 1: Schedule of Assessments

Assessment	SCREENING (2 Weeks)	SINGLE BLIND PLACEBO LEAD-IN (2 Weeks)	DOUBLE-BLIND TREATMENT PHASE									FOLLOW -UP PERIOD ^b (2 Week)
			TITRATION PERIOD ^a (1 Week)			MAINTENANCE PERIOD (12 Weeks)						
Visit Number	1	2	3 Baseline	Call/ Email	4	5	6	7	8	9	10 Study Completion / Early Withdrawal	11
Study Time Point	Week -4 to -2	Week -2	Day 1	Day 3 & 6	Day 7	Week 3	Week 5	Week 7	Week 9	Week 11	Week 13	Week 15
Visit Window (Days)	±3	±3	±3	0	0	±3	±3	±3	±3	±3	±3	±3
Informed consent/assent (if appropriate)	X											
Medical/surgical history	X											
Demographics	X											
Review of inclusion and exclusion criteria	X											
Randomization			X									
Physical exam	X	X	X		X	X	X	X	X	X	X	
Record vital signs	X	X	X		X	X	X	X	X	X	X	
Resting 12-lead ECG	X						X		X		X	
Clinical laboratory tests ^d	X					X					X	
Urinalysis	X										X	

Assessment	SCREENING (2 Weeks)	SINGLE BLIND PLACEBO LEAD-IN (2 Weeks)	DOUBLE-BLIND TREATMENT PHASE									FOLLOW -UP PERIOD ^b (2 Week)
			TITRATION PERIOD ^a (1 Week)			MAINTENANCE PERIOD (12 Weeks)						
Visit Number	1	2	3 Baseline	Call/ Email	4	5	6	7	8	9	10 Study Completion / Early Withdrawal	11
Study Time Point	Week -4 to -2	Week -2	Day 1	Day 3 & 6	Day 7	Week 3	Week 5	Week 7	Week 9	Week 11	Week 13	Week 15
Visit Window (Days)	±3	±3	±3	0	0	±3	±3	±3	±3	±3	±3	±3
Urine dipstick for females of childbearing potential only	X										X	
Urine drug screen (drugs of abuse including THC)	X											
Dosing with Study Medication		X	X	X	X	X	X	X	X	X	X	
Dispense/Review/Collect study medication		X	X	X	X	X	X	X	X	X	X	X
Hyperphagia Questionnaire for Clinical Trial (HQ-CT)	X	X	X		X	X	X	X	X	X	X	
Weight	X	X	X		X	X	X	X	X	X	X	
Three Factor Eating Questionnaire (TFEQ- R18)			X			X			X		X	
PROMIS Life Satisfaction and Positive Affect pediatric short- form questionnaires			X			X			X		X	

Assessment	SCREENING (2 Weeks)	SINGLE BLIND PLACEBO LEAD-IN (2 Weeks)	DOUBLE-BLIND TREATMENT PHASE									FOLLOW -UP PERIOD ^b (2 Week)
			TITRATION PERIOD ^a (1 Week)			MAINTENANCE PERIOD (12 Weeks)						
Visit Number	1	2	3 Baseline	Call/ Email	4	5	6	7	8	9	10 Study Completion / Early Withdrawal	11
Study Time Point	Week -4 to -2	Week -2	Day 1	Day 3 & 6	Day 7	Week 3	Week 5	Week 7	Week 9	Week 11	Week 13	Week 15
Visit Window (Days)	±3	±3	±3	0	0	±3	±3	±3	±3	±3	±3	±3
PROMIS Physical Activity and Fatigue pediatric short-form questionnaires			X			X			X		X	
Patient Global Impression of Severity (PGI-S)			X									
Patient Global Impression of Change (PGI-C)						X			X		X	
DEXA scan ^c			X								X	
Columbia Suicide Severity Rating Scale (C-SSRS)			X								X	
Review of concomitant medications	X	X	X	X	X	X	X	X	X	X	X	X
Review of adverse events	X	X	X	X	X	X	X	X	X	X	X	X
Pharmacokinetics ^c			X				X		X		X	

DEXA = Dual energy X-ray absorptiometry; PROMIS = Patient-Reported Outcomes Measurement Information System

^a Titration schedule = Days 1-3: 20 mg/kg/day; Days 4-6: 30 mg/kg/day; Day 7: 40 mg/kg/day. Phone calls will be made at Day 3 and Day 6 to determine if the patient’s dose may be titrated to the next dose level.

^b The Follow-up Visit is only for patients who do not choose to enroll in the long-term safety study and are tapering off the study drug. Patients will return to the site for assessment of concomitant medications, AEs, and to return and reconcile study drug.

^c Blood draws for trough pharmacokinetic analyses of CBD and metabolite 7-OH-CBD will be collected prior to morning dose at Visit 3 (Baseline) and Visit 6, 8, and 10 during the Maintenance Period.

^d Blood and urine samples for hematology, chemistry, and urinalysis will be collected at Screening (visit1), and Study Completion (Visit 10)/Early Withdrawal. Blood sample for complete blood count (CBC) will be collected at Week 3 (Visit 5).

^e DEXA scan will be completed on a subset of 20 patients.

TABLE OF CONTENTS

PROTOCOL APPROVAL PAGE	2
PROTOCOL SYNOPSIS	3
TABLE OF CONTENTS.....	14
LIST OF TABLES	19
LIST OF FIGURES	19
LIST OF ABBREVIATIONS AND DEFINITIONS OF TERMS.....	20
1. INTRODUCTION	23
1.1. Cannabidiol.....	23
1.1.1. Mechanism of Action	24
1.1.2. Metabolism and Potential Drug Interactions	24
1.2. Nonclinical Experience.....	24
1.2.1. Safety	24
1.2.2. Efficacy.....	25
1.2.2.1. Single Dose Regimens	25
1.2.2.2. Multiple Dose Regimens	26
1.3. Clinical Experience.....	26
1.3.1. Pharmacokinetics	28
1.3.2. Overview of Safety	29
1.3.3. Clinical Safety Data.....	29
1.4. Prader-Willi Syndrome.....	32

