3.2. Patient Selection

3.2.1. Inclusion Criteria

All patients must satisfy the following criteria to be considered for study participation:

1. Patient and/or parent(s)/caregiver(s) fully comprehend the informed consent form (ICF) and assent form, understand all study procedures, and can communicate satisfactorily with the investigator and study coordinator, in accordance with applicable laws, regulations, and local requirements.
2. Males and females from 8-17 years of age, inclusive.
3. Genetically confirmed diagnosis of Prader-Willi Syndrome using standard DNA methylation test or fluorescent *in situ* hybridization. Documentation of genetically confirmed diagnosis of Prader-Willi Syndrome is acceptable.
4. A score of ≥ 10 on the HQ-CT.
5. A caregiver is available to complete the HQ-CT.
6. If female, is either not of childbearing potential (defined as premenarchal or surgically sterile [bilateral tubal ligation, bilateral oophorectomy, or hysterectomy]) or practicing one of the following medically acceptable methods of birth control:
 - a. Hormonal methods such as oral, implantable, injectable, vaginal ring, or transdermal contraceptives for a minimum of 1 full cycle (based on the patient's usual menstrual cycle period) before study drug administration.
 - b. Total abstinence from sexual intercourse since the last menses before study drug administration.
 - c. Intrauterine device.
 - d. Double-barrier method (condoms, sponge, or diaphragm with spermicidal jellies or cream).
7. Adequate renal function, defined as serum creatinine $\leq 1.5 \times$ upper limit of normal (ULN) and urine protein/creatinine ratio < 0.2 .
8. Adequate hepatic function, defined as total bilirubin $\leq 1.5 \times$ ULN and aspartate aminotransferase (AST) and Alanine aminotransferase (ALT) levels $\leq 3 \times$ ULN.
9. Growth hormone treatment will be permitted if doses have been stable for at least 1 month prior to screening.
10. Psychotropic treatment will be permitted and should be stable at least 6 weeks prior to screening.
11. Any other treatment including thyroid hormones should be stable for at least 6 weeks prior to screening.

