3.2.2. Exclusion Criteria

Patients will be excluded for any of the following:

1. Known use of cannabis or cannabinoid-containing products for 4 weeks prior to baseline.
2. History of chronic liver disease, such as cirrhosis or chronic hepatitis due to any cause, or suspected alcohol abuse.
3. Use of weight loss agents or drugs known to affect appetite (including glucagon-like peptide-1[GLP-1] analogs) within 2 months prior to screening.
4. Uncontrolled Type I and Type II diabetes.
5. Currently taking concomitant medications that are strong cytochrome P450 3A4 (CYP3A4) or CYP2D6 inhibitors; or inducers of CYP3A4- or CYP2D6-sensitive substrates with a narrow therapeutic index.
6. Co-morbid condition or disease (such as respiratory disease, heart disease, or psychiatric disorder) diagnosed less than 1 month prior to screening.
7. History or presence of gastrointestinal or any other condition known to interfere with the absorption, distribution, metabolism or excretion of drugs as determined by the Investigator.
8. Patients who have participated in any other trials involving an investigational product or device within 30 days of screening or longer as required by local regulations.
9. Clinically significant abnormalities on ECG at screening or other evidence of heart disease as determined by the Investigator.
10. Has screening systolic blood pressure ≥ 160 mm Hg and diastolic blood pressure > 100 mm Hg (may be repeated one additional time after 5 minutes' rest to verify). Patients with hypertensive levels lower than those specified may be excluded at the Investigator's discretion if deemed to be in the best interest of the patient.
11. Currently taking felbamate.
12. Uncontrolled sleep apnea.
13. Pregnant or lactating female.
14. History of hypersensitivity to drugs with a similar chemical structure or class as CBD.
15. Unwillingness or inability to follow the procedures outlined in the protocol.
16. Patient judged by the investigator or sponsor (or designee) as unable to comply with the treatment protocol, including appropriate supportive care, follow-up and research tests.
17. Positive drug screen, including THC, at time of screening.
18. Creatinine clearance test of < 30 mL/min.

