6.2.3. Vital Signs

Vital signs (seated blood pressure, pulse rate, temperature and respiration rate) will be measured at every visit: Screening (Visit 1), Placebo Lead-In (Visit 2), Baseline (Visit 3), Titration Period (Visit 4), Maintenance Period (Visits 5, 6, 7, 8, 9), and Study Completion/Early Withdrawal (Visit 10) Visits.

Additional vital sign measurements may be performed as deemed medically necessary by research personnel.

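### Exclusion 10 joins its systolic and diastolic limits with *and*, so a child far above only one of them (185/95 or 150/115) does not have to be excluded

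*Protocol*

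**What the plan says.** Exclusion 10 appears twice in the protocol, in the synopsis list ("Has screening systolic blood pressure ≥ 160 mm Hg and diastolic blood pressure >100 mm Hg") and in section 3.2.2 ("Has screening systolic blood pressure ≥ 160 mm Hg and diastolic blood pressure > 100 mm Hg"). Apart from a space, the wording is the same. The reading may be repeated once after five minutes' rest. The criterion then continues: "Patients with hypertensive levels lower than those specified may be excluded at the" investigator's discretion, if that is judged best for the patient.

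Section 3.2.2 opens with "Patients will be excluded for any of the following", so each listed item is mandatory once it is met and has no force until then.

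The other provisions that could bear on a hypertensive child are these:

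- Exclusion 9: "Clinically significant abnormalities on ECG at screening or other evidence of heart disease as determined by the Investigator".
- Exclusion 6: "Co-morbid condition or disease (such as respiratory disease, heart disease, or psychiatric disorder) diagnosed less than 1 month prior to screening".
- Inclusion 11: "Any other treatment including thyroid hormones should be stable for at least 6 weeks prior to screening".
- Section 6.2.3: "Vital signs (seated blood pressure, pulse rate, temperature and respiration rate) will be measured at every visit". Section 6.2.2 likewise requires a physical examination at each visit.

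None of them contains a blood-pressure value.

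**The concern.** In an exclusion criterion, *and* narrows the rule: both parts must be true before the patient is kept out. A blood-pressure safety limit is normally meant to work the other way, with either component enough. As worded, marked isolated systolic or isolated diastolic hypertension falls outside the mandatory rule and is left to an optional sentence.

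This is the only numeric blood-pressure limit for entry in a trial of 8- to 17-year-olds whom section 1.5 expects to be obese. With about 10 sites, the same reading could be a screen failure at one and a randomized patient at another. The issue is baseline safety and uniform eligibility. It does not depend on any claim that cannabidiol raises blood pressure.

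**Working it through.** The plan gives no figure to reproduce here. The check is to apply the criterion as a logical rule and then look for any other provision that would catch the same child.

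**Step 1: the rule as written against the alternative.** The inputs are the two limits in exclusion 10: SBP ≥ 160 and DBP > 100 mm Hg. The readings are examples chosen to test the rule.

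| Reading (mm Hg) | SBP − 160 | DBP − 100 | Excluded under *and* | Excluded under *or* |
|---|---|---|---|---|
| 185/95 | +25 | −5 | no | yes |
| 150/115 | −10 | +15 | no | yes |
| 160/100 | 0 | 0 | no | yes |
| 159/101 | −1 | +1 | no | yes |
| 160/101 | 0 | +1 | yes | yes |
| 170/110 | +10 | +10 | yes | yes |
| 150/95 | −10 | −5 | no | no |

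Two limits, each met or not met, give 2 × 2 = 4 combinations. Exclusion is mandatory in 1 under *and* and in 3 under *or*. The gap is 3 − 1 = 2 combinations, the two isolated elevations. Within them the mandatory rule has no upper systolic bound while DBP stays at or below 100, and no upper diastolic bound while SBP stays below 160.

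**Step 2: does usage elsewhere settle the meaning?** It does not.

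- Section 3.6 uses *and* as a strict joint condition in a liver stopping rule (ALT or AST above 3 × ULN together with a second abnormality).
- Exclusion 4 uses *and* between type I and type II diabetes, where either would be expected to count.
- Inclusions 7 and 8 join pairs of laboratory limits with *and*. In an inclusion criterion that means failing either limit keeps the child out, the opposite of its effect in an exclusion. The same construction may have been carried across, but the documents do not say so.

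**Step 3: does another provision close the gap?**

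- The discretion sentence is permissive. It refers to levels lower than those specified, which fits 185/95 poorly because 185 is above the stated systolic limit.
- Exclusions 9 and 6 are mandatory once met, but they turn on an ECG finding, heart disease or a recently diagnosed condition. An isolated high reading first found at screening need not meet either.
- Inclusion 11 concerns stability of existing treatment, so it does not reach an untreated child.
- Blood pressure is recorded at every visit, but no action threshold is attached. The numeric stopping rules in section 3.6 are all hepatic.
- The schedule of assessments places eligibility review at Screening only.

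**The case against.** The strongest reply is that the case is already covered. The specified level is a pair of values, so a reading that fails one half can be called lower than specified, and the investigator may then exclude. Sites may also read *and* loosely, as exclusion 4 invites, and apply *or* already. After screening, the two-week placebo lead-in brings blood-pressure measurement and physical examination at Visit 2 and again at Visit 3, before any active drug. Sections 3.3 and 3.4 let the investigator or sponsor withdraw a patient whose safety is in doubt. Finally, changing to *or* still leaves every reading below both limits to discretion.

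Much of this is fair and keeps the point small. The extra visits and withdrawal powers are real safeguards. None of them supplies a mandatory threshold, however, and a rule that protects patients only if sites read it against its wording should be reworded. That discretion remains below both limits is also true, but the criterion intends that.

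It could also be said that cannabidiol is not known to affect blood pressure. Section 1.3.3 cites no effect at 1200 mg/day for up to 20 days in people with cannabis-smoking experience. At 40 mg/kg/day a child above 1200 / 40 = 30 kg exceeds that dose (above 1200 / 30 = 40 kg at the reduced dose), and maintenance lasts 12 × 7 = 84 days, so that report does not cover this exposure. The sponsor's 48-week study at up to 40 mg/kg/day was described as generally well tolerated, though that is not a blood-pressure finding. Neither source decides the question, which is who may enter.

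**Conclusion.** The concern holds. As worded in both places, exclusion 10 is mandatory only for combined elevation, and marked isolated systolic or diastolic hypertension is left to optional site judgement. No other provision in the protocol or SAP sets a blood-pressure limit for entry.

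The size is limited to the rule itself: two of four combinations are left uncovered. The number of children involved cannot be estimated, since the documents report no blood-pressure distribution, and 66 is the number to be enrolled and randomized, not screened. The conclusion rests on reading the criterion literally. The documents do not state whether *and* or *or* was meant, although *or* seems the likelier intent. This is a minor correction to an eligibility rule. The HQ-CT primary analysis, its power and its type I error are unaffected, and the values 160 and 100 are not disputed.

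**What to change.** In exclusion 10, replace *and* with *or* between the two limits, in the synopsis and in section 3.2.2, so that breaching either one excludes after the permitted repeat reading. Reword the discretion sentence to apply to readings below both limits. If the joint condition really was intended, state that explicitly and say what a site must do with a reading above only one limit.

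The drafting cost is one word in two places plus the small clarification. There may be a few additional screen failures. Their number cannot be estimated, and some of these children might have been excluded by discretion anyway. Because section 9.3 does not allow rescreening, the single repeat reading is their only second chance, so sites should be reminded to use it.
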